APPENDIX 12 EuroQoL 5-Dimension (EQ5D)

By placing a tick in one box in each group below, please indicate which statements best describe your own health state today.

Mobility

- I have no problems in walking about
- I have some problems in walking about
- I am confined to bed

Self-Care

- I have no problems with self-care
- I have some problems washing or dressing myself
- I am unable to wash or dress myself

Usual Activities *(e.g. work, study, housework, family or leisure activities)*

- I have no problems with performing my usual activities
- I have some problems with performing my usual activities
- I am unable to perform my usual activities

Pain/Discomfort

- I have no pain or discomfort
- I have moderate pain or discomfort
- I have extreme pain or discomfort

Anxiety/Depression

- I am not anxious or depressed
- I am moderately anxious or depressed
- I am extremely anxious or depressed

To help people say how good or bad a health state is, we have drawn a scale (rather like a thermometer) on which the best state you can imagine is marked **100** and the worst state you can imagine is marked **0**.

We would like you to indicate on this scale how good or bad your own health is today, in your opinion. Please do this by drawing a line from the box below to whichever point on the scale indicates how good or bad your health state is today.

**Your own
health state
today**

AD	Atopic Dermatitis
ADA	Anti-Drug Antibody
AE	Adverse Event
AESI	Adverse Event of Special Interest
AIC	Akaike's Information Criterion
ALT	Alanine Aminotransferase
ANCOVA	Analysis of Covariance
ANOVA	Analysis of Variance
AST	Aspartate Aminotransferase
ATC	Anatomical Therapeutic Chemical
AUC	Area under the Curve
BLQ	Below the Limit of Quantification
BMI	Body Mass Index
bpm	Beats per Minute
BSA	Body Surface Area
CI	Confidence Interval
Cmax	Maximum Concentration
CMH	Cochran-Mantel-Haenszel
CPK	Creatinine Phosphokinase
CRO	Contract Research Organization
CSR	Clinical Study Report
DLQI	Dermatology Life Quality Index
DPS	Dynamic Pruritus Scale
EASI	Eczema Area and Severity Index
ECG	Electrocardiogram
eCRF	electronic Case Report Forms
EMA	European Medicines Agency
EQ5D	EuroQoL 5-Dimension
FDA	Food and Drug Administration
HADS	Hospital Anxiety and Depression Scale

Abbreviation	Term
HSV	Health State Value
ICF	Informed Consent Form
ICH	International Conference on Harmonisation
IDMC	Independent Data Monitoring Committee
IGA	Investigator's Global Assessment
IL	Interleukin
IRR	Injection-related Reaction
ITT	Intent-to-treat; intention-to-treat
IVRS	Interactive Voice Response System
IWRS	Interactive Web Response System
KM	Kaplan-Meier
LOCF	Last Observation Carried Forward
LSmean	Least Square Mean
MedDRA	Medical Dictionary for Regulatory Activities
MI	Multiple Imputation
mL	Milliliter
MMRM	Mixed-effect Model for Repeated Measures
NCA	Non compartmental analysis
NRS	Numeric Rating Scale
OC	Observe Case
PCS	Pruritus Categorical Scale
PCSV	Potentially Clinically Significant Value
PD	Pharmacodynamics
PEF	Peak Expiratory Flow
PK	Pharmacokinetics
PP	Per-Protocol
PT	Preferred Term
Q1	Lower quartile
Q3	Upper quartile
Q4W	Every 4 weeks
QoL	Quality of Life

Abbreviation	Term
REML	Restricted Maximum Likelihood
ROC	Receiver Operating Characteristic
SAE	Serious Adverse Event
SAF	Safety (analysis population)
SAP	Statistical Analysis Plan
SCORAD	SCORing Atopic Dermatitis
SD	Standard Deviation
SOC	System Organ Class
SUSAR	Suspected Unexpected Serious Adverse Reaction
TARC	thymus and activation-regulated chemokine
TB	Tuberculosis
TCI	Topical Calcineurin Inhibitor
TCS	Topical Corticosteroid
TEAE	Treatment-emergent Adverse Event
TESAE	Treatment-emergent Serious Adverse Event
TFL	Tables, Figures, and Listings
ULN	Upper Limit of Normal
UN	Unstructured
WBC	White Blood Cell
VAS	Visual Analogue Scale
WHODD	the World Health Organization Drug Dictionary

1 INTRODUCTION

This Statistical Analysis Plan (SAP) describes the planned analysis and reporting for GALDERMA R&D, SNC, protocol RD.03.SPR.114322, entitled “A randomized, double-blind, multi-center, parallel-group, placebo-controlled dose-ranging study to assess the efficacy and safety of nemolizumab (CD14152) in moderate-to-severe atopic dermatitis subjects with severe pruritus receiving topical corticosteroids”, Version 01 dated October 23, 2017.

Atopic dermatitis (AD) is a chronic inflammatory skin disease characterized by pruritus (itching), xerosis (skin dryness) and eczematous lesions. AD is currently managed with topical treatments and, when they are not sufficient to control the disease in moderate to severe AD, by systemic treatments, as well as phototherapy. Given the high response variability and the known secondary adverse effects of these drugs, there is a need for new drugs to better control the disease of moderate to severe patients while decreasing the risk of secondary adverse effects. Nemolizumab, a humanized anti-human interleukin (IL)-31 receptor A monoclonal antibody, could decrease pruritus and improve AD in these patients and therefore represent a new treatment option. Subjects with insufficient response to topical therapies and severe pruritus, which leads to extensive scratching further aggravating the disease, could particularly benefit from such a therapy.

This study is conducted to evaluate the efficacy, safety and pharmacokinetics (PK) of multiple subcutaneous doses of nemolizumab in the treatment of AD, when administered on top of background topical corticosteroid (TCS). Three doses have been selected to fully explore the dose range and enable selection of dose(s) for Phase 3 development.

The planned analyses identified in this SAP may be included in the clinical study report (CSR), regulatory submissions, or future manuscripts. Also, post hoc exploratory analyses not necessarily identified in this SAP may be performed to further examine study data. Any post hoc, or unplanned, exploratory analyses performed, if included, will be clearly identified as such in the final CSR.

This SAP is based upon the following study documents:

- Study protocol, Version 01 (23 October 2017)
- Electronic Case Report Form (eCRF), Version 5.0 (19 February 2018)

The structure and content of this SAP provides sufficient detail to meet the requirements identified by the Food and Drug Administration (FDA), European Medicines Agency (EMA), and International Conference on Harmonisation (ICH) of Technical Requirements for Registration of Pharmaceuticals for Human Use: Guidance on Statistical Principles in Clinical Trials. All work planned and reported for this SAP will follow internationally accepted guidelines, e.g., Ethical Guidelines for Statistical Practice published by the American Statistical Association and Code of Conduct published by the Royal Statistical Society, for statistical practice.

The reader of this SAP is encouraged to also read the clinical protocol, and other relevant documents for details on the planned conduct of this study. Other than the schedule of assessments which is provided in Appendix 1, operational aspects related to collection and timing of planned clinical assessments are not repeated in this SAP unless relevant to the planned analyses.

2 STUDY OBJECTIVES

2.1 Primary Objective

The primary objective is to assess the efficacy of several subcutaneous doses of nemolizumab compared to placebo in moderate-to-severe AD subjects with severe pruritus receiving TCS, who were not adequately controlled with topical treatments.

2.2 Secondary Objectives

The secondary objectives are to evaluate the safety of nemolizumab and to characterize its PK profile.

3 INVESTIGATIONAL PLAN

3.1 Overall Study Design and Plan

This is a randomized, placebo-controlled, double-blind, parallel-group, dose-ranging, phase 2b study to evaluate the efficacy and safety of various doses of nemolizumab in moderate-to-severe AD subjects with severe pruritus. The duration of this clinical trial is up to 36 weeks for a given subject, including a 2 to 4-week run-in period, a 24-week treatment period and an 8 week follow-up period (12 weeks after the last study drug administration).

Eligible subjects must have moderate-to-severe AD, severe pruritus and a documented history of inadequate response to topical AD medications. Subjects meeting the inclusion/exclusion criteria at the screening visit will receive background therapy of AD (including a moisturizer, a medium potency TCS for the body, and a low potency TCS for the face, neck etc.) to be used throughout the study. Subjects who still meet the inclusion/exclusion criteria at the baseline visit will be randomized in a 1:1:1:1 ratio to either of the 3 groups of nemolizumab or placebo. Randomization will be stratified by AD severity based on the baseline Investigator's Global Assessment (IGA) scores (3 or 4). Injection of study drug will occur every 4 weeks (Q4w, at weeks 4, 8, 12, 16 & 20). A loading dose will be administered on day 1 for the groups of 10 mg and 30 mg only (20 mg and 60 mg, respectively), while for 90 mg group, the same dose will be administered at each injection visit.

An independent Data Monitoring Committee (IDMC) will be set-up to monitor safety data generated in this clinical trial on an ongoing basis and make appropriate recommendations to the sponsor.

Assessments of efficacy, safety and PK will be conducted throughout this clinical trial. Refer to Appendix 1 for the complete schedule of assessments.

3.2 Efficacy and Safety Variables

3.2.1 Efficacy Variables

3.2.1.1 Eczema Area and Severity Index (EASI)

EASI is a composite score ranging from 0 to 72. The severity of erythema, induration/papulation, excoriation, and lichenification will be assessed by the investigator or trained designee on a scale of 0 (absent) to 3 (severe) for each of the 4 body areas: head/neck, trunk, upper limbs, and lower limbs, with half points allowed. In addition, the extent of AD involvement in each of the 4 body areas will be assessed as a percentage by body area of head, trunk, upper limbs and lower limbs, and converted to a score of 0 to 6. The EASI score will be calculated in the eCRF as follows.

Body region	EASI score
Head/Neck (H)	$(E + I + Ex + L) \times Area \times 0.1$
Upper limbs (UL)	$(E + I + Ex + L) \times Area \times 0.2$
Trunk (T)	$(E + I + Ex + L) \times Area \times 0.3$
Lower limbs (LL)	$(E + I + Ex + L) \times Area \times 0.4$
EASI =	Sum of the above 4 body region scores

The degree of severity of each sign (E=erythema, I=induration/papulation, Ex=excoriation, L=lichenification) in each of the 4 body regions is evaluated based on a scale ranging from 0 to 3 (0: none; 1: mild; 2: moderate; 3: severe), with half points allowed.

Area (the affected body area) is defined as follows: 0= 0%; 1=1-9%; 2=10-29%; 3=30-49%; 4=50-69%; 5=70-89%; 6=90-100%. Among the 4 zones, trunk includes the genital area, and lower limbs include the buttocks.

The EASI will be assessed at screening, baseline, weeks 1, 2, 4, 8, 12, 16, 20, 24, 28, 32, or early termination and/or unscheduled visits when applicable.

3.2.1.2 Investigator's Global Assessment (IGA)

IGA is a 5-point scale ranging from 0 (clear) to 4 (severe) used by the investigator or trained designee to evaluate the global severity of AD.

The IGA will be assessed at screening, baseline, weeks 1, 2, 4, 8, 12, 16, 20, 24, 28, 32, or early termination and/or unscheduled visits when applicable.

3.2.1.3 Body Surface Area (BSA)

The BSA involvement of AD will be assessed by the investigator or trained designee for each part of the body (the possible highest score for each region is: head and neck [9%], anterior trunk [18%], back [18%], upper limbs [18%], lower limbs [36%], and genitals [1%]), and will be reported as a percentage of all major body sections combined.

The BSA will be assessed at screening, baseline, weeks 1, 2, 4, 8, 12, 16, 20, 24, 28, 32, or early termination and/or unscheduled visits when applicable.

3.2.1.4 SCORing Atopic Dermatitis (SCORAD)

SCORAD ranges from 0 to 103 and has 3 components: extent (BSA, as described in Section 3.2.1.3), signs and symptoms of AD, and subjective symptoms (European task force on atopic dermatitis 1993). Investigator or designee will assess the severity of 6 signs of AD (erythema/darkening, edema/papulation, oozing/crusting, excoriation, lichenification/prurigo and dryness), each on a scale ranging from 0 (none) to 3 (severe). Investigator or designee will also ask the subjects to evaluate their symptoms of pruritus and sleep loss (average for the last 3 days/nights), each evaluated on a Visual Analogue Scale (VAS) from 0 to 10. The SCORAD score will be calculated in the eCRF as follows.

SCORAD score $\frac{A + B + C}{3}$

where: A = Extent of AD, B = Intensity of AD, C = Subjective symptoms (itch and sleeplessness).

The maximum SCORAD score is 103. The SCORAD will be assessed at baseline, weeks 1, 2, 4, 8, 12, 16, 20, 24, 28, 32, or early termination and/or unscheduled visits when applicable.

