Appendix 4 EQ5D Index Score

The EQ5D consists of the EQ5D descriptive system and the EQ VAS. The descriptive system is made up of 5 dimensions: mobility, self-care, usual activities, pain/discomfort and anxiety/depression. Each dimension has 3 levels: no problems, some problems, extreme problems (see scoring algorithm below). A unique health state is defined by combining 1 level from each of the 5 dimensions. There are 243 possible health states defined on this way. Each state is referred to in terms of a 5 digit code. Any missing values which are coded as '9' will be set to missing (and hence no health state value will be calculated). Ambiguous values (e.g., 2 boxes ticked for a single dimension) should be treated as missing values. If 1 or more domains are missing the health state value (HSV) will not be calculated.

For example, if a subject provides the following responses: Mobility=No problems, Self-care=No problems, Usual Activities=Some problems, Pain/Discomfort=Moderate problems, Anxiety/Depression=Extreme problems, his response sequence is 11223. The 243 theoretical possible sequences can then be mapped to a HSV to provide a summary across all dimensions. The tariff to be used for the mapping is that given by Dolan (1997). The scoring algorithm is as follows (the value set for UK is used in calculating EQ5D on this study):

Full health (11111)	1.000
Constant term (for any dysfunctional state)	-0.081
Mobility level 1	0
Mobility level 2	-0.069
Mobility level 3	-0.314
Self-care level 1	0
Self-care level 2	-0.104
Self-care level 3	-0.214
Usual activities level 1	0
Usual activities level 2	-0.036
Usual activities level 3	-0.094
Pain/discomfort level 1	0
Pain/discomfort level 2	-0.123
Pain/discomfort level 3	-0.386
Anxiety/depression level 1	0
Anxiety/depression level 4	-0.071
Anxiety/depression level 3	-0.236
At least one domain at 3 (N3)	-0.269

The HSV for the subject with example sequence 11223 = 0.255, calculated as follows:

- 1) Full health =1
- 2) Minus constant: -0.081
- 3) Minus mobility level 1: 0
- 4) Minus self-care level 1: 0
- 5) Minus usual activities level 2: -0.036
- 6) Minus pain/discomfort level 2: -0.123
- 7) Minus anxiety/depression level 3: -0.236
- 8) Minus N3: -0.269

Where level 1 corresponds to no problems, level 2 to some problems, and level 3 to extreme problems.

Reference

Dolan P. Modeling valuations for EuroQol health states. Med Care, 1997; 35(11):1095-108.

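### As printed, the SAP's EQ5D table weights an anxiety/depression level that cannot occur, and its SCORAD formula cannot reach the stated maximum of 103

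*SAP*

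**What the plan says.** **EQ5D.** SAP Appendix 4 states: "Each dimension has 3 levels: no problems, some problems, extreme problems". It counts 243 possible health states on that basis. Its table of decrements lists levels 1, 2 and 3 for mobility, self-care, usual activities and pain/discomfort. For anxiety/depression the rows are level 1 (0), "Anxiety/depression level 4" (-0.071) and level 3 (-0.236); there is no level 2 row. The appendix names a published UK tariff as the source of the weights. Change in the index at week 24 is analysed by ANCOVA (SAP 4.9.3.4).

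**SCORAD.** SAP 3.2.1.4 says that the eCRF calculates the score, and then shows "SCORAD score $\frac{A + B + C}{3" with the key "where: A = Extent of AD, B = Intensity of AD, C = Subjective symptoms (itch and sleeplessness". The same section adds: "The maximum SCORAD score is 103". Protocol Appendix 4 gives A/5 + 7B/2 + C for the same three components, and Protocol 7.1.1.4 gives the range as 0 to 103. Absolute and percent change in SCORAD at week 24 are secondary endpoints (Protocol 7.1.2.2, SAP 3.2.2.2), analysed by MMRM (SAP 4.7.3.9).

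SAP 4.11, which lists departures from the protocol's planned analysis, mentions neither score.

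**The concern.** Each rule conflicts with statements in its own section. A three-level instrument cannot produce a level 4 response, and the level that subjects can choose has no weight. A formula that averages the three SCORAD components cannot reach the maximum stated beside it, and it is not the protocol's formula.

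A SCORAD derived or checked by the SAP line would be on a different scale with different component weights, so neither absolute nor percent change would match the protocol's endpoint. For EQ5D, the SAP table is the only set of index weights in the two documents (the questionnaire in Protocol Appendix 12 carries none), so a programmer has nothing else there to fall back on.

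**Working it through.** **SCORAD: component maxima**

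- A (extent) is the BSA percentage. SAP 3.2.1.3 caps the regions at "head and neck [9%], anterior trunk [18%], back [18%], upper limbs [18%], lower limbs [36%], and genitals [1" percent: 9 + 18 + 18 + 18 + 36 + 1 = 100.
- B (intensity): "Investigator or designee will assess the severity of 6 signs of AD", "each on a scale ranging from 0 (none) to 3 (severe"), so 6 × 3 = 18.
- C (symptoms): pruritus and sleep loss, each on a 0 to 10 VAS, so 2 × 10 = 20.

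**SCORAD: does either formula give the stated 103?**

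- Protocol Appendix 4: 100/5 + 7 × 18/2 + 20 = 20 + 63 + 20 = 103. It does.
- SAP 3.2.1.4 as extracted: (100 + 18 + 20)/3 = 138/3 = 46. It does not.
- SAP line without the divisor: 100 + 18 + 20 = 138. It does not.

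**SCORAD: is the difference only a rescaling?** The share of the maximum from extent, intensity and symptoms is:

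- SAP line: 100/138, 18/138 and 20/138, or 72%, 13% and 14%.
- Protocol formula: 20/103, 63/103 and 20/103, or 19%, 61% and 19%.

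The shares differ, so percent change differs too. Two illustrations, with component values that are assumed and not taken from the documents:

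| A/B/C, baseline to later visit | SAP line | Protocol formula |
|---|---|---|
| 40/12/14 to 35/4/4 | 22.0 to 14.3, -34.8% | 64 to 25, -60.9% |
| 40/12/14 to 10/8/10 | 22.0 to 9.3, -57.6% | 64 to 40, -37.5% |

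The discrepancy can go in either direction, depending on which component improves.

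**EQ5D: the SAP's worked example.** State 11223: 1 - 0.081 - 0.036 - 0.123 - 0.236 - 0.269 = 0.255, as the SAP states. The example has anxiety/depression at level 3, so it never uses the mislabelled row and cannot expose it.

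**EQ5D: effect of the row.**

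- Three levels in five dimensions give 3^5 = 243 states, matching the SAP. Of these, 3^4 = 81 have anxiety/depression at level 2.
- State 11112 with -0.071 applied to level 2: 1 - 0.081 - 0.071 = 0.848.
- State 11112 with no term for level 2: 1 - 0.081 = 0.919, which is 0.071 higher. If a missing weight is instead treated as an error, the state has no score.
- Move from 11112 to 11111 with the term dropped: 1.000 - 0.919 = 0.081, from the constant, instead of 1.000 - 0.848 = 0.152.
- Move from 11122 to 11121 with the term dropped: 1 - 0.081 - 0.123 = 0.796 in both states, so no change registers. With the weight in place, 0.796 - 0.071 = 0.725 rises to 0.796.

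**The case against.** The strongest objection concerns the SCORAD equation. It is a typeset formula read from PDF, it lacks an equals sign, and other formulas in the SAP are redacted (4.6) or missing (4.9.1). The surrounding text twice gives 103 as the top of the scale and uses the same three components as the protocol. A damaged equation explains this at least as well as an authoring error, and the documents cannot settle which it is. This stands, and it is why the source PDF must be checked before anything is changed.

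Second, the score is calculated automatically in the eCRF (Protocol 11.5.2), the protocol's formula is sound, and the SAP introduction cites an existing eCRF version as one of its bases. A reader might infer that SCORAD results will be wrong; the documents do not show that. In the other direction, SAP 3.2.1.4 presents its line as the eCRF calculation, so agreement should be verified and not assumed.

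Third, the EQ5D entry is a label slip that its own appendix largely resolves: the row sits where level 2 belongs, and the closing note equates level 2 with some problems. A programmer may well read it correctly. Anxiety and depression are also covered elsewhere, by the separate EQ5D dimension analyses (SAP 4.9.3.4) and by HADS (SAP 4.9.3.2). This lowers the stakes but leaves the printed table wrong.

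**Conclusion.** Both rules are wrong as written, with minor to moderate severity. The EQ5D fault is plain table text and the firmer of the two; it stands whatever the source PDF shows for SCORAD. The SCORAD fault is conditional on the equation being printed as extracted, and its effect is conditional on the eCRF or a derived dataset having been built from it.

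Three stronger readings are not supported:

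- A reader might infer that the EQ5D index would miss every move from level 2 to level 1 in anxiety/depression. That fails for 11112 to 11111, where the constant still registers 0.081; it holds only if the term is dropped and another dimension remains impaired.
- A reader might infer that every level 2 subject scores 0.071 too high. That assumes the term is silently dropped; the state could equally be unscorable.
- A reader might infer from the 72% share that the SAP formula would mainly measure body surface area in this trial. That share describes the theoretical range, not the variance or expected change among the subjects.

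That -0.071 belongs to level 2 is inferred from the missing row and its position; the cited tariff was not available to confirm the value. The primary endpoint (EASI), its dose-response test and the sample size are unaffected.

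**What to change.** - **EQ5D.** In SAP Appendix 4, confirm -0.071 against the tariff that the SAP cites and relabel the row as level 2. Add a second worked example with anxiety/depression at level 2, such as 11112 = 0.848 if the value is confirmed, so that the row is tested.
- **SCORAD.** Check the equation in SAP 3.2.1.4 in the source PDF. If it is printed as (A+B+C)/3, replace it with A/5 + 7B/2 + C, as in Protocol Appendix 4. If it is a reading artefact, the SAP text needs no change.
- **Verification.** Before database lock, recompute SCORAD from the recorded components (Protocol 11.5.2 requires them on a separate source document) and compare it with the eCRF values. Check the programmed EQ5D index for level 2 responses.

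The cost is at most two lines of SAP text, one added example and two derivation checks. No data collection, sample size or analysis model changes.

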3.2.1.5 Pruritus Numeric Rating Scale (NRS)

Pruritus NRS is a scale to be used by the subjects to report the intensity of their pruritus (itch) during the last 24 hours on a scale of 0 to 10. Subjects will record their pruritus NRS scores (average itch intensity and maximum itch intensity during the previous 24 hours) on an electronic device, and will complete the assessment once daily in the evening throughout the clinical trial (including the run-in and the follow-up period).

Weekly prorated average score will be calculated and used in the analysis. If a subject has less than 4 diary entries in a week, the weekly average scores will be set to missing. Refer to Section 4.2 for classification of diary data into analysis week/visit.

